Based on our surgical team's previous experience with off-pump implantation of Jarvik 2000 (Jarvik Heart, Inc., New York, NY) in animals (22) and humans (23), we started implanting HVADs without CPB in 2011 (11). Our goal was to implant HVAD off-CPB when possible. The decision to implant an LVAD on-CPB was made intraoperatively if patient developed hemodynamic instability during positioning of the heart. We have previously showed that LVAD implantation without the use of CPB helps to minimize post-operative complications without hemodynamic compromise or excessive bleeding during implantation (6).

Left Ventricular Assist Devices and Right Ventricular Dysfunction

Outcomes after LVAD implantation are critically dependent on right ventricular (RV) function. This means that the ability of the RV to keep up with the improved blood flow following LVAD greatly effects how well a person does following surgery. It is understood that a high pulmonary artery (PA) pressure (pressure in the blood vessel that takes blood from the right side of the heart to the lungs) measured before surgery, indicates that a higher risk of right heart failure (RHF) exists after LVAD implantation. Development of RHF in LVAD patients has a direct effect on mortality and is associated with a prolonged ICU stay and hospital admission (24). RHF in LVAD patients leads to increased morbidity and is associated with worse outcomes after cardiac transplantation (25). Despite improvements in surgical and medical management the incidence of RHF after LVAD implantation has plateaued at approximately 20-30% (26). The intra-operative technique used during LVAD implantation may play a role in the preservation of RV function. Cross-clamping and cardioplegia may compromise RV contractility (27).

Left Ventricular Assist Devices and Coagulation-Fibrinolysis Changes during On-Pump and Off-Pump LVAD implantation

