Prior to surgery, all consecutive patients scheduled for LVAD implantation will be screened for inclusion into the study. If the patient fulfills the inclusion criteria for the study, he/she will be approached and the study will be described. If the patient agrees to participate, he /she will be given written, informed consent for inclusion in the study. Baseline demographic and clinical characteristics of patients, echocardiographic parameters, hemodynamic data from right heart catheterization and blood samples will be collected. These procedures are a part of standard of care procedures, so the patients will not suffer any discomfort or additional cost due to the inclusion in the study. However, patients will be asked to provide additional blood samples for advanced hemostatic assays and panel reactive antibodies. Randomization is done intraoperatively as detailed later. In cases where the patient will not be eligible for inclusion into the study prior to randomization (e.g. if during the heart positioning the patient becomes hemodynamically unstable and the CPB will a priority have to be used), the additionally collected blood samples will be discarded. The operation is initiated by a standard procedure and all postoperative management will be completed according to institution protocols and standard of care medical guidelines.

Randomization will be done with the help of the REDCap (REDCap electronic data capture tools hosted at UTHealth) (36), a software program that contains a randomization module using stratified randomization (by type of LVAD therapy).

The primary hypothesis is that off-pump LVAD surgery compared with on-pump LVAD surgery reduces a composite outcome of right ventricular dysfunction, thrombotic complications and survival in the short term (30 days) and that these benefits are maintained at long term (1 year). The secondary hypothesis is that off-pump LVAD surgery compared with on-pump LVAD surgery reduces OHP leading to lower complement activation and reduced immune allosensitization in the short term (30 days) and at long term (1 year).

Inclusion criteria

- Adult (≥ 18 years of age)
- The patient has had a diagnosis of end stage heart failure, NYHA class III or IV HF for a minimum of 90 days prior to screening.
- The patient has guideline-directed medical therapy according to ACC/AHA/ESC HF guidelines
- The patient has an Interagency Registry for Mechanically Assisted Circulatory Support (INTERMACS) score of 1-3.

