- The patient has peri/postpartum cardiomyopathy, or is a pregnant or lactating woman, or a woman of child-bearing age not using a suitable method of contraception.
- The patient, who in the absence of an ICD (or any implanted device capable of defibrillation), has a history of malignant ventricular arrhythmia or sustained ventricular tachycardia (VT), with sustained VT demonstrated by QRS complexes wider than 120 milliseconds, lasting more than 30 seconds, and with a rate of more than 100 beats per minute on screening ECG or other data supporting this diagnosis.
- Recent history of psychiatric disease, including drug or alcohol abuse, that is likely to impair, in the opinion of the investigator, the subject's ability to comply with protocol-mandated procedures.
- Participation in any other clinical investigation that is likely to confound study results or affect study outcome

DEFINITION OF OUTCOME MEASURES

Primary Outcome Measures

Occurrence of the composite outcome of moderate or severe RV dysfunction (perioperative right heart failure), severe renal dysfunction requiring renal replacement therapy, thrombotic complications or death from any cause within 30 days post LVAD implantation, defined as:

- **Perioperative RV failure** is defined by the INTERMACS scoring as the need for intravenous inotropes for >14 days post-operatively or a right ventricular assist device (RVAD) (37). Right ventricular function will be measured by tricuspid annular plane systolic excursion (TAPSE) values assessed using echocardiography prior to implantation (baseline), 14 (+/- 2 days) days post-implant, 30-days post-implant, 6-months and 1-year post-implant. Additionally, we will collect also hemodynamic evidence of RV dysfunction with: a right-atrial pressure (RAP): pulmonary capillary wedge pressure (PCWP) ratio of ≥ 0.67 .
- **A thrombotic complication** is defined as any thromboembolic event (transient ischemic attack or stroke objectively confirmed with computed tomography) or confirmed pump thrombus as previously done (38). A suspected pump thrombosis event in which a thrombus is confirmed in

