Per standard of care, every subject receives a **transthoracic echocardiogram (TTE)** within 48 hours prior to LVAD implantation (baseline). These preoperative echocardiograms are reviewed and compared with echocardiograms at 30 (+/- 5) days, 6-months and 1-year post-LVAD implantation. The echocardiograms will be performed by staff cardiologists at UTHealth/Memorial Hermann Hospital-TMC and are regularly scheduled per standard of care. The staff cardiologists will not be aware of the treatment assignment of enrolled patients.

For each subject, the following echocardiographic parameters will be pulled from the electronic medical record and transferred to case report forms:

- left ventricular end-systolic diameter (LVESD)
- left ventricular end-diastolic diameter (LVEDD)
- left ventricular (LV) ejection fraction
- severity of mitral regurgitation (MR) based on a graded system
- RV ejection fraction (RVEF),
- RV end-diastolic dimension (RVEDD),
- RV end-systolic diameter (LVESD)
- RV stroke work index (RVSWI),
- tricuspid annular plane systolic excursion (TAPSE)
- severity of tricuspid regurgitation (TR)

Right heart catheterization is another standard diagnostic procedure for LVAD patients. The test evaluates the hemodynamics of LVAD patients. Right heart catheter hemodynamic variables are analyzed pre-LVAD implantation and compared with 30 (+/- 5) days, 6-months and 1-year post-LVAD implantation values as regularly scheduled care. All procedures will be performed by staff cardiologists at UTHealth/Memorial Hermann Hospital-TMC, who will not be aware of the treatment assignments.

For each subject, the following hemodynamic measurements will be pulled from the electronic medical record and transferred to case report forms:

- central venous pressure (CVP),
- pulmonary artery pressures (PAP): systolic and diastolic PAP,
- pulmonary capillary wedge pressure (PCWP),
- cardiac index (CI)
- pulmonary vascular resistance (PVR)
- right-atrial pressure (RAP)
- RAP: pulmonary capillary wedge pressure (PCWP) ratio

Laboratory parameters: Per standard of care, blood for routine biochemical and coagulation markers will be taken at prior to surgery (within 48 hours) and at follow-up visits (30 days, 6 months, 1 year). The electronic medical record will be used to ascertain the results of the following laboratory tests:

- complete blood count
- blood glucose
- hemoglobin A1c
- total cholesterol
- LDL cholesterol
- HDL cholesterol
- triglycerides
- creatinine

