Preparation of buffy coat: Buffy coat will be removed after the first spinning of the centrifuge and decanted into Eppendorf tubes. The remaining packed RBCs in tubes will be stored for later (storage at -80°C).

DETERMINATION OF ALLOANTIBODIES

The measurement and assessment of alloantibodies is now a standard of care test performed on patients scheduled for LVAD surgery. A single-bead antigen assay on the Luminex platform (One Lambda Inc., Canoga Park, CA) is used at the institution. Mean fluorescence intensity (MFI) >4,000 is considered the threshold of clinical significance. Whenever the alloantibodies and panel reactive antibody status (PRAs) are measured, the data will be transferred from the medical record to the case report forms.

Calculated PRA (cPRA) values will be obtained using the United Network of Organ Sharing cPRA calculator. Sensitization will be defined as cPRA >10%. LVAD-associated sensitization will be defined as cPRA >10% documented after LVAD implantation in patients with cPRA <10% before LVAD implantation.

STATISTICAL METHODS

We calculated a sample size of 140 patients (70 in each arm), which will provide 80% power to detect a 30% relative risk reduction for the composite primary outcome at 30 days. The intention-to-treat principle, in which all participants will be included in their assigned treatment groups regardless of actual surgical procedure performed, will guide all analyses.

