Data will be represented as frequency distributions and percentages. Values of continuous variables will be expressed as mean \pm standard deviation and median with interquartile range, as necessary. Continuous variables will be compared using independent samples t-tests or Wilcoxon rank-sum tests, where appropriate. Categorical variables will be compared by means of χ^2 tests or Fischer's exact test, where appropriate. Hemodynamic variables between ON-pump and OFF-pump procedures will be compared with Kruskal-Wallis tests. To analyze changes in echocardiographic and hemodynamic parameters and laboratory values, McNemar matched-pairs tests will be used to compare preoperative values to postoperative values after matching individual patient data. For all analyses, a $p < 0.05$ will be considered statistically significant. Kaplan-Meier analysis will be used to calculate survival along with a log-rank p value when comparing ON-pump and OFF-pump groups. Actuarial survival at 30-days, 6-months and 1-year post-implantation will be calculated by constructing life tables. All data will be analyzed using STATA 15 software (STATA, 2017, College Station, TX).

EXPECTED RESULTS AND IMPORTANCE OF THE STUDY

As LVADs become a more widely used and accepted treatment option for patients with refractory, end-stage heart failure, it will be necessary to further optimize outcomes and reduce the incidence of postoperative complications. We believe that using off-pump LVAD implantation will significantly reduce transfusion requirements, right ventricular dysfunction and alloantibody formation. We expect that in the off-pump group, there will be less exposure to blood products, which will lead to reduced immunosenzitization. If this research finds that off-pump use can decrease the morbidity and mortality in this patient population, it will greatly influence the manner in which these patients are managed. This would reduce hospitalizations and delays in subsequent transplant planning. This would not only be of great benefit to the patient but would significantly decrease health-care costs.

RISK AND BENEFITS

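### The 30-day composite would be tested without adjustment, although the protocol names preoperative PA pressure as a marker of right heart failure and records it: a modest, avoidable loss of precision

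*Combined protocol and SAP*

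**What the plan says.** All references are to the combined protocol and SAP.

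- **Primary outcome** (Definition of Outcome Measures): a yes/no endpoint within 30 days, which also counts all-cause mortality: "Occurrence of the composite outcome of moderate or severe RV dysfunction (perioperative right heart failure), severe renal dysfunction requiring renal replacement therapy, thrombotic complications".
- **Test** (Statistical Methods): none is named for this endpoint. The applicable rule is general: "Categorical variables will be compared by means of" chi-square or Fisher's exact tests. No regression model, covariate or stratified test is planned for any outcome. Haemodynamic values appear in the analysis only as quantities to be compared, not as baseline covariates.
- **Prognosis** (Background, on right ventricular dysfunction): a high PA pressure "measured before surgery, indicates that a higher risk of right heart failure (RHF) exists after LVAD implantation". The same section puts right heart failure at roughly 20-30%.
- **Data** (Collection of Basic Data): "Right heart catheter hemodynamic variables are analyzed pre-LVAD implantation", and the list for each subject includes "pulmonary artery pressures (PAP): systolic and diastolic PAP".
- **Randomisation** (Study Design and Patients; Surgical Technique): intraoperative, stratified only by type of LVAD therapy.
- **Sample size** (Statistical Methods): 70 per arm, "which will provide 80% power to detect a 30% relative risk reduction for the composite primary outcome at 30 days". The on-pump event rate behind this is not given.

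**The concern.** The protocol identifies a baseline measurement that carries information on part of its primary endpoint, collects it before assignment, and then does not use it. PA pressure is not balanced by design, because the only stratification factor is the type of LVAD therapy. In a trial of 140 patients it can differ between arms by chance and push the crude result either way.

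Two things are at stake. One is some efficiency. The other is the credibility of the primary result if the baseline table shows unequal PA pressure. An adjustment chosen after that table has been seen would look selective, so it has to be fixed beforehand.

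**Working it through.** **1. The plan's own figure.** For two proportions with pooled variance and two-sided 5%:

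n per arm = [1.96·√(2·p̄(1−p̄)) + 0.8416·√(p₁(1−p₁)+p₂(1−p₂))]² / (p₁−p₂)², with p₂ = 0.7·p₁.

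The on-pump rate p₁ is not stated, so it was solved for. At p₁ = 0.752: p₂ = 0.5264, p̄ = 0.6392, difference 0.2256. The numerator is (1.331 + 0.556)² = 3.56, and 3.56 / 0.0509 gives 70. The stated 80% power therefore needs an on-pump rate of about 75%. With 70 per arm, power is 23% at a 30% rate and 32% at a 40% rate.

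**2. Chance imbalance.** The SD of the between-arm difference in a standardised covariate is √(2/70) = 0.169. Then 0.33/0.169 = 1.95, and the two-sided probability of a larger gap is 0.051, about 1 trial in 20.

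At an assumed OR of 2 per SD and a 40% event rate, the average slope is 0.150 per SD. A 0.33 SD gap shifts the crude risk difference by 0.150 × 0.33 = 0.050, or 5 points. The targeted difference at that rate is 0.3 × 40 = 12 points. At a 30% rate the shift is 4.4 points against a target of 9.

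**3. Power if the covariate predicts the whole composite.** Simulation: 70 per arm, one standard normal baseline covariate, 30% relative reduction, two-sided 5%, 6,000 to 20,000 runs per setting. The crude chi-square is compared with a logistic score test adjusted for the covariate. The ORs per SD are assumptions; the documents give none. Entries are crude → adjusted power (%).

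| On-pump rate | OR 1.5 | OR 2 | OR 3 |
|---|---|---|---|
| 30% | 23.5 → 23.9 | 23.5 → 24.9 | 23.0 → 26.8 |
| 40% | 32.9 → 34.0 | 32.2 → 35.1 | 32.0 → 38.3 |
| 75.2% | 81.0 → 82.1 | 79.7 → 83.8 | 79.6 → 87.6 |

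A separate run with a Wald test (4,000 runs per setting) gave gains of 0 to 5 points at 30-40%, against 0.4 to 6.3 above. The simulation error of each power figure is about √(0.32×0.68/6000) = 0.6 points. With no treatment effect (30% rate), rejection was 5.0-5.1% crude and 4.6-5.1% adjusted.

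**4. Power if the covariate predicts only right heart failure.** Assume right heart failure at 25%, the midpoint of 20-30%, with the other components independent of PA pressure. At a 75% composite rate, at least 75 − 25 = 50 points of events then involve no right heart failure. ORs of 1.5 / 2 / 3 for right heart failure shrink to about 1.14 / 1.24 / 1.36 for the composite. Crude → adjusted power (%), 8,000 runs:

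| Composite rate | OR 1.5 | OR 2 | OR 3 |
|---|---|---|---|
| 40% | 33.0 → 33.5 | 31.6 → 32.5 | 32.4 → 34.8 |
| 75% | 80.0 → 80.6 | 79.9 → 80.5 | 80.4 → 81.4 |

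The gain is about 0 to 2 points.

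**5. Events available.** At 30% versus 21%: 70 × 0.30 + 70 × 0.21 = 21 + 14.7, about 36 events. That supports only a short covariate list.

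**The case against.** The case against acting is substantial, and much of it stands.

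- **The crude test is valid.** Randomisation protects its overall type I error, and its p-value and confidence interval already allow for chance imbalance. A reader might infer that an unadjusted primary test is biased or invalid; nothing in the documents or the simulations supports that. What remains is the single trial with a visible imbalance, where adjustment helps and must be pre-specified.
- **The link is to one component only.** The Background ties PA pressure to right heart failure, not to renal replacement therapy, thrombosis or death. It is tempting to quote power rising from 80% to 87%, but that needs an OR of 3 per SD acting on the whole composite at a 75% on-pump rate. The documents state neither.
- **Other RV measures.** A reader might also infer that the protocol names TAPSE and the RAP:PCWP ratio as predictors. It does not: the outcome definitions use them as measures or evidence of RV function.
- **The prognostic spread may be narrow.** Severe tricuspid regurgitation and planned RV support are excluded, and only patients stable on heart positioning are randomised. Catheterisation has no stated baseline window, unlike the 48 hours for echocardiography, and some patients may be measured on mechanical support. These points weaken the likely gain but do not reverse it: with no prognostic value (OR 1.0), adjustment brought no gain and no material loss.
- **The primary test is inferred.** The plan never assigns chi-square or Fisher's test to the composite. This is true, and it is a further reason to name the analysis.

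**Conclusion.** The point holds as a modest improvement, not as a defect of validity. The only analysis on offer for the primary composite ignores a baseline value that the protocol itself calls a marker of right heart failure and already collects.

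The better-supported loss is protection from chance imbalance: a shift of about 5 points in roughly 1 trial in 20, at OR 2 per SD for the whole composite and a 40% rate. The power gain is about 0 to 6 points at 30-40% on-pump rates and 1 to 8 points at 75% if the covariate predicts the whole composite. It is about 0 to 2 points if PA pressure predicts right heart failure alone. All these sizes rest on assumed ORs.

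A reader might hope that adjustment rescues the sample size. It does not: at a 40% rate the best adjusted power above is 38.3%, and the unstated control rate behind the 80% figure is a separate and larger problem.

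**What to change.** In Statistical Methods, name the primary analysis of the 30-day composite:

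- a logistic model with arm, baseline systolic PA pressure (continuous) and the randomisation stratum;
- results as a standardised (marginal) risk difference and risk ratio, each with a 95% CI;
- a simple rule for missing baseline PA pressure, for example single imputation that ignores arm;
- the crude chi-square or Fisher's test as supportive.

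A second RV covariate is optional. If one is used, it should be a single measure named in advance, because of the limited event count, and not described as a predictor that the protocol identifies. The simulations above cover one covariate with arm, so the final model, including the stratum, should be checked the same way before it is fixed.

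The cost is SAP wording only: no extra patients, visits or data. The small downside is that a model replaces a 2×2 table.

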LVADs have been implicated as one of the key causes of allosensitization in patients awaiting cardiac transplantation. Contemporary data on allosensitization triggered by CF-LVADs are limited, and whether allosensitization attributes to CF-LVADs affects outcomes after transplant remains controversial (33). In a recent study, an adjusted multivariable Cox regression analysis included the variables of LVAD implantation, leukocyte-filtered packed red blood cell and platelet transfusion, and sex; it found that LVAD implantation was the only independent predictor of sensitization (34). Significant allosensitization developed in 22% of the patients who received LVADs, with calculated panel reactive antibodies (PRA) > 10%.

The effect of on-pump versus off-pump implantation has not been studied, yet. However, several investigators found reduced blood loss or less need for transfusions after off-pump cardiac surgery (35). The reduction of the number of transfusions with off-pump LVAD surgery could potentially attenuate the development of antibodies to blood products that would make future transfusions and heart transplantation less difficult.

METHODS

STUDY DESIGN AND PATIENTS

LVAD-ON-OFF is a single center, two-arm, parallel-group, individually randomized (1:1) controlled trial with blinded outcome assessment (at 30 days, 6 months and 1 year) which aims to compare adverse events after off-pump versus on-pump LVAD implantation.

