To evaluate the role of CPB on hemostatic and fibrinolytic parameters, we will make sure that the perioperative level of heparinization will be comparable between groups.

All patients will be postoperatively treated with 81mg aspirin daily and coumadin with a target international normalized ratio range of 2.0–2.5. Data on the use of antithrombotic therapy will be recorded at baseline and at each follow-up appointment. Time-in-Therapeutic Range (TTR) will be calculated using the Rosendaal method as a measure of quality of anticoagulation dose management (42).

Use of tranexamic acid

Tranexamic acid is a well-documented fibrinolytic inhibitor. The medical team will be advised to use always the same dose of tranexamic acid (if the patient's condition will allow it) in the perioperative period as it has an effect on overall fibrinolytic potential.

SELECTION OF SURGEONS

All surgical procedures will be performed by an "experienced" cardiac surgeon with more than 5 years of practice in cardiac surgery after residency training and has performed more than 100 LVAD implantations. Primary surgeons have experience with both techniques (on-pump and off-pump LVAD implantation). All procedures will be done under the supervision of an "expert" cardiac surgeon ([name]/PI of this protocol) who has more than 30 years of experience in advanced and complex cases of cardiac surgery, has performed more than 500 LVAD implantations, and is very experienced with both techniques (on-pump and off-pump LVAD implantation). Residents and fellows will not be eligible to participate as primary surgeons in the trial.

BLOOD COLLECTION AND PREPARATION

For research purposes, two additional vials of blood will be collected at the same time that standard of care blood draws are done. The timepoints for the research blood draws will be at baseline (within 48 hours of surgery), within 24-48 hours post-operation (but before discharge), 30 days, 6 months and 1 year. For the follow-up blood draws (+/- 5 days is acceptable).

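### No planned analysis gives a baseline-adjusted between-arm effect for OHP or the supportive continuous measures, although their baselines are collected

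*Combined protocol and SAP*

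**What the plan says.** All of the analysis text is in Statistical Methods. Between arms, the general rule is "Continuous variables will be compared using independent samples t-tests or Wilcoxon rank-sum tests, where appropriate". Catheter data have their own sentence: "Hemodynamic variables between ON-pump and OFF-pump procedures will be compared with Kruskal-Wallis tests". Change is handled separately: "To analyze changes in echocardiographic and hemodynamic parameters and laboratory values, McNemar matched-pairs tests will be used to compare preoperative values to postoperative values". That last sentence compares time points within patients and does not mention treatment arm. No ANCOVA, regression, mixed model, baseline covariate or between-arm comparison of change appears anywhere in the document.

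The baselines exist. Under Collection of Basic Data/Patient Characteristics, "Right heart catheter hemodynamic variables are analyzed pre-LVAD implantation and compared with 30 (+/- 5) days, 6-months and 1-year post-LVAD implantation values". The same section schedules echocardiograms and routine laboratory tests before surgery and at follow-up. For the research samples, Blood Collection and Preparation states "The timepoints for the research blood draws will be at baseline (within 48 hours of surgery" and then lists 24-48 hours, 30 days, 6 months and 1 year. Definition of Outcome Measures schedules TAPSE at baseline and four later times.

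OHP is secondary outcome 5, and the secondary hypothesis is that off-pump surgery lowers it relative to on-pump surgery. It has no analysis sentence of its own, so it falls under the general rule for continuous variables.

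**The concern.** The trial's questions about OHP and right ventricular function are between-arm questions. A preoperative-versus-postoperative test shows whether values moved after LVAD implantation, in patients who all received an LVAD. It does not show whether they moved differently with and without bypass. Replacing McNemar with a paired test suited to continuous data would not change that, because there would still be no arm term.

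The tests that do compare arms have no place for the patient's own starting value. Where baseline predicts follow-up, that leaves explainable variation in the error term. At stake is the precision of the OHP comparison and of the supportive measures (TAPSE, the RAP:PCWP ratio, other echo, catheter and laboratory values), in a trial of 140 patients with little precision to spare. Choosing a covariate model after the arm-level data have been seen would also be open to the charge of selection.

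**Working it through.** **The plan's own figure.** The only stated calculation concerns the binary 30-day composite: "We calculated a sample size of 140 patients (70 in each arm), which will provide 80% power to detect a 30% relative risk reduction". It cannot be reproduced because no control event rate is given, and it does not bear on this point. The plan gives no power or detectable difference for any continuous measure, so the figures below are new.

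**Inputs from the documents.** 70 per arm; "individually randomized (1:1) controlled trial"; significance level 0.05 ("For all analyses, a $p < 0.05$ will be considered statistically significant").

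**Assumptions.** Two-sided testing (sidedness is not stated); all 140 patients measured; roughly normal data with a linear baseline/follow-up relation; and a correlation ρ between baseline and follow-up of 0.2, 0.3, 0.5 or 0.7. The documents give no ρ.

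**Step 1: which planned analyses contain both arm and baseline?**
- t-test, Wilcoxon: arm yes, baseline none specified.
- Kruskal-Wallis: the same. With two groups it is equivalent to the Wilcoxon rank-sum test, so it adds nothing.
- McNemar preoperative versus postoperative: baseline yes, arm no.

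None contains both.

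**Step 2: detectable difference without adjustment.** By normal approximation, (1.960 + 0.842) × √(2/70) = 0.474 SD. The exact two-sample t-test gives 0.477 SD. For the rank tests under normality, 0.477/√(3/π) = 0.477/0.977 = 0.488 SD. SD is the within-arm SD of the follow-up value.

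**Step 3: with ANCOVA.** The variance of the arm difference is multiplied by 1 − ρ², and the detectable difference by √(1 − ρ²).

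| ρ | 1 − ρ² | Variance cut | Detectable difference, 80% power | Power for 0.4 SD |
|---|---|---|---|---|
| unadjusted | 1 | none | 0.477 SD | 65% |
| 0.2 | 0.96 | 4% | 0.477 × 0.980 = 0.467 SD | 67% |
| 0.3 | 0.91 | 9% | 0.477 × 0.954 = 0.455 SD | 69% |
| 0.5 | 0.75 | 25% | 0.477 × 0.866 = 0.413 SD | 77% |
| 0.7 | 0.51 | 49% | 0.477 × 0.714 = 0.341 SD | 91% |

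**Step 4: if change scores were intended.** A between-arm comparison of changes has variance 2(1 − ρ) relative to follow-up only: 1.6, 1.4, 1.0 and 0.6 at the four correlations. It is worse than follow-up alone below ρ = 0.5. It never beats ANCOVA, because 1 − ρ² = (1 − ρ)(1 + ρ) and 1 + ρ cannot exceed 2. So ANCOVA is at least as precise under either reading of the plan.

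**The case against.** The strongest reply is that this concerns efficiency and not validity. Under 1:1 randomisation an unadjusted comparison is unbiased, and its type I error already allows for chance baseline imbalance. That stands. A reader might infer that the planned comparisons are biased; the documents do not support that.

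A reader might also infer that the plan compares raw follow-up values and throws baseline away. The text does not say so. It refers only to continuous and haemodynamic variables, and a change score could be read in. What can be said is that none is specified and no adjusted effect is planned.

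The reach is narrower than the list of measurements suggests. OHP is the only formally listed continuous outcome with a baseline. Chest tube output, operating and ventilation times, lengths of stay and nitric oxide use have none. TAPSE and RAP:PCWP sit under the right ventricular failure definition as supporting measurements, and the other echo, catheter and laboratory values are not listed outcomes. So it would be too strong to say that every mechanism outcome suffers.

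The correlation could be low for OHP in particular. Heparin, tranexamic acid, and then aspirin and coumadin all come between baseline and later samples. At ρ of 0.2 or less the gain is 4% of variance or less. That is why the range starts at 0.2.

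Finally, separate preoperative-versus-postoperative tests in each arm would invite the false reading that significance in one arm alone shows a difference. The plan does not say the tests are run per arm, so this is not counted as a harm of the written plan.

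**Conclusion.** The point holds in a limited form. As written, the plan yields no baseline-adjusted between-arm effect for OHP or for the supportive continuous measures, although the data to produce one are collected. The planned comparison is valid but less precise than it could be. The loss ranges from slight (4% of variance at ρ = 0.2; detectable difference 0.48 to 0.47 SD) to substantial (49% at ρ = 0.7; 0.48 to 0.34 SD). Where a given measure falls depends on a correlation the documents do not give. Deaths, transplants and missed catheterisations would raise every detectable difference; with equal numbers analysed, the proportional gain stays 1 − ρ². The primary composite and its sample size are not touched. The change should be made because it is nearly free, not because the planned tests mislead.

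**What to change.** In Statistical Methods, state that for each continuous measure with a preoperative value (OHP and its coagulation and fibrinolytic components, TAPSE, RAP:PCWP, and the other echo, catheter and laboratory values) the between-arm analysis at each postoperative visit is an ANCOVA. It regresses the follow-up value on arm, baseline value and the randomisation stratum actually used, and reports the adjusted difference with its 95% CI. Two details need settling in the text:

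- **Transformation.** Fix any log or rank transformation variable by variable before arm-level data are seen, not according to how the trial data look.
- **Stratum.** The design section stratifies by type of LVAD therapy, which could mean the device or bridge versus destination intent. Say which was programmed in REDCap and use that.

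Keep the Wilcoxon and Kruskal-Wallis comparisons as supportive, and label the preoperative-versus-postoperative comparison as descriptive only. The cost is a few sentences of plan text and slightly more analysis work, with no new patients, visits or samples.
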